12 SAFETY ANALYSES

12.1 Treatment Emergent Adverse Events

Only treatment-emergent AEs, defined as any event that is temporally associated with administration of study product, will be summarized in tables. Events prior to treatment (e.g., due to study-related procedure) will be listed in an appendix to the final study report. DLTs will be listed.

The following tables of AE data will be created to summarize the number and percent of patients who experience at least one event of each of the following types:

- All AEs
- Drug-related AEs
- AEs by CTCAE Grade
- Drug related AEs by CTCAE Grade
- AEs with CTCAE Grade severity \geq Grade 3
- Drug-related AEs with CTCAE Grade severity \geq Grade 3
- SAEs (this may be a listing if there are few events)
- Drug-related SAEs
- Fatal AEs (this may be a listing if there are few events)
- AEs that result in study discontinuation
- AEs that lead to withdrawal of study drug
- AEs categorized as AESI and/or IREs

Tabulated data will display the number and percent of patients that experience individual events by System Organ Class (SOC) and Preferred Term (PT). Events will be displayed alphabetically for SOC and in descending order of overall PT incidence within each SOC.

An overall summary of AEs will display the number and percent of patients who experience at least one event of each of the following types:

- Any AE
- Any drug-related AE
- Any AE with CTCAE Grade severity \geq Grade 3
- Any drug-related AE with CTCAE Grade severity \geq Grade 3
- Any SAE
- Any drug-related SAE

- Any AE that results in study or study drug discontinuation
- Any fatal AE
- Any AESI
- Any IREs

The following AESI will be summarized:

- All cytokine release syndrome or infusion related reaction events
- Grade 2 or greater immune-related AEs including, but not limited to, events of pneumonitis, colitis, autoimmune hepatitis, arthritis, glomerulonephritis, myocarditis and cardiomyopathy, hypophysitis, or thyroiditis
- Tumor lysis syndrome (TLS)
- Neutropenic sepsis/fungemia
- Grade 2 or greater neurological events.
- Capillary leak syndrome
- Epstein-Barr Virus (EBV) reactivation

The following summaries will be provided for AESI:

- All AESI
- Study drug related AESI
- Serious AESI
- Study drug related serious AESI
- AESI with CTCAE grade of Grade ≥ 3
- Study drug related AEs with CTCAE severity Grade ≥ 3

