## 6.4.4 Immune-related Adverse Experiences

Immune checkpoint blockade has been associated with several syndromes resulting from the breaking of immunological tolerance (42). Although not observed in non-clinical studies to date, similar immunomodulation might be expected with flotetuzumab. These syndromes include: pneumonitis, colitis, autoimmune hepatitis, arthritis, glomerulonephritis, myocarditis and cardiomyopathy, hypophysitis, or thyroiditis. Immune related adverse experiences will be considered AESIs (Section 7.11.3). Their occurrence dictates interruption, and potentially discontinuation, of study drug administration pending further evaluation.

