#### **Immediately Reportable Event**

Immediately reportable events (IREs) are events that must be reported immediately to MacroGenics Product Safety or designee within 24 hours of being identified (see Section 7.12). IREs include but are not limited to:

- SAEs
- AEs leading to permanent discontinuation of study drug in an individual patient
- Pregnancy in a study patient or partner (Note: If the female partner of a male patient becomes pregnant, the partner must be requested to complete a Pregnant Partner Consent Form so that pregnant partner, fetal and/or newborn information can be collected.) Upon confirmation of serum pregnancy testing, the patient will be followed for the outcome of pregnancy. All live newborns will be followed six months after the birth, and all necessary information will be collected to assess the effects of study drug on the newborn. If necessary, the follow-up period will be extended for the newborn.
- Grade 2 or higher infusion-related reactions including CRS
- TLS as defined in Section 6.4.2
- Neutropenic sepsis or fungemia as defined in Section 6.4.3

- Immune related adverse events as defined in Section 6.4.4
- Grade 2 or higher neurological events as described in Section 6.4.5
- Capillary leak syndrome as described in Section 6.4.6
- EBV reactivation as described in Section 6.4.7
- Confirmed or presumed (test pending/clinical suspicion) SARS-CoV-2 infection.

Withdrawal of patient from study drug administration due to toxicity (e.g., AE, SAE, AESI) or pregnancy.

In those cases in which the IRE is considered related to study drug and the event is of sufficient clinical concern, the study drug may be discontinued and the patient will continue participation in the study for observational safety and analysis (except for cases where the patient is withdrawn from the study by the Investigator). At any time after completion of the study, if an Investigator becomes aware of a SAE that s/he suspects is related to study drug, the Investigator should report the event to MacroGenics Product Safety or designee.

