# 7.11.3 Adverse Events of Special Interest

In this study, TLS (as defined in Section 6.4.2), neutropenic sepsis/fungemia (Section 6.4.3), immune-related events (Section 6.4.4), treatment-related  $\geq$  Grade 2 neurological events (Section 6.4.5), capillary leak syndrome (Section 6.4.6), and EBV reactivation (Section 6.4.7) are considered AESIs and should be reported as IREs and documented on the appropriate eCRF irrespective of attribution to flotetuzumab.

All infusion related reactions including CRS are considered AESIs and should be documented on the appropriate eCRF; only  $\geq$  Grade 2 events need to be reported to the Sponsor as IREs.

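### The SAP summarises immune-related AESIs only from Grade 2 upward, whereas the protocol makes them AESIs at every grade

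*SAP*

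**What the plan says.** **Immune-related events, protocol.** Section 6.4.4 states that "Immune related adverse experiences will be considered AESIs", with no grade attached. Section 7.11.3 repeats them in its AESI list, also without a grade, and the IRE list in Section 7.11.1 includes them on the same terms.

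**Immune-related events, SAP.** Section 12.1 introduces its list with "The following AESI will be summarized". The immune-related line in that list reads "Grade 2 or greater immune-related AEs including, but not limited to, events of pneumonitis", followed by further examples of the same kind as those in protocol 6.4.4.

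**Neurological events.** The protocol 7.11.3 list runs "immune-related events (Section 6.4.4), treatment-related", and the next item is neurological events of Grade 2 or higher. The sentence closes by saying that the listed events "are considered AESIs and should be reported as IREs and documented on the appropriate eCRF irrespective of attribution to flotetuzumab". The IRE list in 7.11.1 asks for "Grade 2 or higher neurological events as described in Section 6.4.5", with no attribution condition. SAP 12.1 likewise sets a Grade 2 threshold and no attribution condition.

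**The concern.** The AESI tables are where a reader looks for the risks the sponsor singled out in advance. If the SAP uses a narrower definition than the protocol and gives no reason, the report can show fewer AESIs than the protocol says occurred.

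The protocol does not treat these events as incidental. Section 7.11.1 makes them reportable within 24 hours, and 6.4.4 attaches a consequence for study drug to their occurrence, in both cases at any grade. The absence of a threshold also looks deliberate, because 7.11.3 sets thresholds where it wants them: Grade 2 for neurological events, and Grade 2 for immediate reporting of infusion-related reactions and cytokine release syndrome (IRR/CRS), while keeping every grade of IRR/CRS as an AESI.

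SAP 12.1 also asks for several outputs that carry an AESI count: an overall 'Any AESI' row, a table of events categorised as AESI and/or IRE, and a dedicated 'All AESI' summary. It does not say whether these draw on the eCRF designation, which follows the protocol, or on the SAP's own list. The same report could therefore carry two different AESI totals.

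**Working it through.** No sample size, error rate or event count is involved, so the check is a comparison of definitions.

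**Step 1: compare the categories.** Protocol 7.11.3 and SAP 12.1 name the same seven.

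| AESI category | Protocol 7.11.3 | SAP 12.1 | In protocol set but not in SAP set |
|---|---|---|---|
| IRR/CRS | all grades | all grades | none |
| Immune-related | all grades | Grade 2 or above | **Grade 1** |
| Tumor lysis syndrome | no grade limit | no grade limit | none |
| Neutropenic sepsis/fungemia | no grade limit | no grade limit | none |
| Neurological | Grade 2 or above; attribution wording inconsistent | Grade 2 or above, any attribution | none |
| Capillary leak syndrome | no grade limit | no grade limit | none |
| EBV reactivation | no grade limit | no grade limit | none |

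Six of the seven lose nothing. Only the immune-related line is narrower in the SAP.

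**Step 2: the neurological line under both readings.** Reading A takes the opening restriction in 7.11.3 at face value: related events of Grade 2 or above. Reading B follows the closing clause and 7.11.1: all events of Grade 2 or above. The SAP set is all events of Grade 2 or above. Reading A is contained in it and reading B equals it, so the SAP omits nothing on either reading.

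**Step 3: which outputs can change.** SAP 12.1 plans six dedicated AESI summaries. Two are restricted to Grade 3 or above and cannot change. The other four (all, drug-related, serious, drug-related serious) can. The serious rows are included because protocol 7.11.1 lets a Grade 1 event be serious through hospitalisation.

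**Step 4: where a Grade 1 immune-related event still appears.** It is an IRE under protocol 7.11.1. Provided it is treatment-emergent, it therefore belongs in the SAP's 'Any IREs' row and its table of events categorised as AESI and/or IRE, as well as in the all-event and by-grade tables. Those outputs keep the event, but a table by preferred term cannot rebuild the number of patients with an AESI.

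**Step 5: size.** The documents give no rate for Grade 1 immune-related events. Two features of the text point to a small effect:
- Protocol 7.11.4 says Grade 1 laboratory findings generally need not be reported as adverse events unless clinically significant, so some would never enter the database as events.
- A patient-level 'Any AESI' count changes only for a patient with no other AESI. IRR/CRS of any grade already qualifies, and protocol 6.4.1.2 describes it as common.

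The loss would therefore show mainly in the immune-related line itself.

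**The case against.** The strongest reply is that nothing is really lost. Grade 1 immune-related events remain in the IRE outputs and the general tables. A SAP may summarise a graded subset. Whether 'Any AESI' is affected depends on programming specifications that SAP Section 14 places in a separate document. Most of this stands. It limits the point to the summaries built from the SAP list, and it means a loss in the 'Any AESI' row is possible but not established. It does not explain the threshold: SAP 12.1 gives no reason for it and does not present it as a subset of a wider protocol definition.

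Two stronger readings are tempting, and the documents support neither.

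- A reader might infer that Grade 1 immune-related events disappear from the report. They do not, because they are IREs and adverse events and are tabulated as such.
- A reader might infer that the attribution clash in 7.11.3 also shrinks the SAP's neurological AESI counts. It does not, because the SAP rule has no attribution condition. A site applying the treatment-related restriction literally could leave an unrelated event off its AESI page. However, 7.11.1 separately requires Grade 2 or higher neurological events to be reported whatever their cause, and Section 7.12 requires all adverse events on the eCRF. Any effect is confined to how a site records the AESI designation.

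**Conclusion.** The concern holds for immune-related events. SAP 12.1 defines a narrower AESI set than protocol 6.4.4 and 7.11.3, and the difference is exactly the Grade 1 events. Four of the six dedicated AESI summaries can be affected if they are built from the SAP list. The 'Any AESI' row is affected only if it is built the same way, which the SAP does not state. The number of events is unknown and may be small.

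The conclusion assumes that some Grade 1 immune-related events are recorded as treatment-emergent adverse events, and that the SAP list, not the eCRF designation, drives the summaries. If the eCRF designation drives them, the counts would follow the protocol and the SAP list would misdescribe the tables. The wording needs correcting in either case.

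The neurological wording in protocol 7.11.3 is a real inconsistency but a secondary, editorial one. This is a minor point overall: efficacy, power and type I error are unaffected.

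**What to change.** **SAP 12.1.** Delete the Grade 2 threshold from the immune-related line, refer to protocol 6.4.4 for the definition, and present these events by grade. State that 'Any AESI' and 'All AESI' use the protocol 7.11.3 definition, and name the data source for the AESI designation. If the sponsor wants a Grade 2 or higher display as well, it can be added as a stated and justified subset beside the full count. The cost is a short SAP edit, best made before database lock. No new data are needed, because protocol 7.11.3 already requires these events to be documented at every grade. AESI counts may rise slightly.

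**Protocol 7.11.3, at the next amendment.** Reconcile the treatment-related restriction on neurological events with the closing clause on attribution. Removing the restriction would match 7.11.1 and SAP 12.1, and attribution would remain available as a breakdown through the SAP's drug-related AESI summaries. This is a protocol change. Section 11.1 requires sponsor approval and IRB/IEC submission, with prior IRB/IEC approval where required, and the synopsis foresees about 50 institutions. It should therefore be bundled with other changes and not issued alone. It leaves the SAP's neurological rule unchanged.

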12.2 Clinical Laboratory Evaluations

Summaries of laboratory values will display descriptive statistics for numerically quantified labs. Summaries will be grouped by lab panel (e.g., hematology, blood chemistry, and urinalysis) and will be displayed by visit for each lab parameter. Graphs of mean values over time or individual values at each time point may be used.

Shift tables will be used to display the percent of patients who have a shift in their lab values from normal at baseline to each post-baseline visit by CTCAE v4.0 severity Grade.

Listings of all clinical laboratory data with abnormal flags will be provided by patients and tests.

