## **2 BACKGROUND INFORMATION**

## 2.1 Disease Background

## 2.1.1 Acute Myeloid Leukemia

Acute myeloid leukemia (AML) is a heterogeneous group of diseases characterized by infiltration of the blood, bone marrow, and other tissues by neoplastic cells of hematopoietic origin (47). The disease occurs at a rate of 3.5 per 100,000 people per year in the United States (US). Incidence increases with age and the median age at onset is 67 years. Heredity, radiation, chemical and occupational exposures, and drugs (particularly chemotherapeutic agents) have been implicated in the etiology of AML. A number of chromosomal and molecular genetic abnormalities have been described in this disease and subclassification based on these abnormalities is now commonplace. Patients often present with nonspecific symptoms, particularly fatigue and/or unexplained fevers resulting from anemia, leukocytosis, leukopenia or leukocyte dysfunction, and/or thrombocytopenia. Initial physical findings may include splenomegaly, hepatomegaly, lymphadenopathy, sternal tenderness, bleeding or hemorrhage, and/or soft tissue infiltration. Diagnosis depends upon examination of peripheral blood elements or, more importantly, characterization of bone marrow cellularity and composition. Therapy for AML has changed little in the last 30 years. Standard induction therapy usually consists of the "7 + 3" regimen of cytarabine and daunorubicin. This is followed by consolidation therapy that may include hematopoietic stem cell transplantation (HSCT) in high-risk patients. However, outcomes from standard therapy are disappointing. Age limits aggressive treatment for many patients and older patients subjected to aggressive therapy have more resistant disease and a greater likelihood of early demise (1), and even in patients younger than 60 years, remission rates to standard induction therapy are only 65-75%. Half of those who do not reach complete remission experience a fatal complication related to bone marrow aplasia or impaired recovery of normal hematopoiesis and half have chemotherapy resistant disease. Even when patients enter complete remission, the occurrence of relapse is high. Salvage therapies, including stem cell transplantation, have limited impact, and most patients succumb to this disease in short order (5,25,46). New therapies are clearly needed.

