Clinical Laboratory Changes: Safety laboratory assessments will be carried out locally and evaluated by the Investigator to ensure patient safety. The Investigator is responsible for reviewing the results of all laboratory tests as they become available. Laboratory tests will be graded according to CTCAE v4.0. Laboratory values that fall outside of a clinically accepted reference range or values that differ significantly from previous values must be evaluated by the Investigator for clinical significance. The Investigator may repeat the laboratory test or request additional tests to verify the results of the original laboratory tests, in which case the repeat assessment will be considered the true value. If the Investigator determines the laboratory value is an abnormal change from baseline and is of clinical significance for that patient, it is considered an AE. Generally, Grade 1 laboratory findings need not be reported as AEs unless clinically significant. The Investigator will evaluate laboratory findings of  $\geq$  Grade 2 classification to determine their clinical significance and if an AE has occurred. Consistent with the CTCAE designation of Grade 3 events as severe or medically significant and Grade 4 events as life-threatening, all such events should be reported as AEs or SAEs, as appropriate, unless these are considered an expected consequence of the underlying disease. Grade 2 events may be reported as AEs if, in the opinion of the Investigator, the event exhibits clinical significance. If clinically relevant abnormal laboratory values are associated with clinical symptom(s), or consistent with a diagnosis, the diagnosis should be reported as the AE (e.g., hemoglobin 9 g/dl in an adult female = anemia). If these clinically relevant abnormal laboratory values do not result in a diagnosis, the test result or finding should be reported as the AE assuming that it does not represent a laboratory error. Repeat testing may be indicated. Such laboratory values should generally be recorded as "increased" or "decreased" (e.g., change from baseline hemoglobin of 13 g/dl to 11 g/dl = hemoglobin decreased).

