## 9.5.2 Laboratory Values

Summaries of laboratory values will display descriptive statistics for numerically quantified labs. Summaries will be grouped by lab panel (e.g., hematology, blood chemistry, and urinalysis) and will be displayed by visit for each lab parameter. Graphs of mean values over time or individual values at each time point may be used.

Shift tables will be used to display the percent of patients who have a shift in their lab values from normal at baseline to each post-baseline visit by CTCAE v4.0 severity Grade.

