11.2.1 Key Secondary Efficacy Analyses

The key secondary efficacy endpoints include CR rate, CRh rate, duration of response, postbaseline transfusion independence rate, HSCT rate and incidence and duration of hospitalization.

Duration of response (DOR) will be calculated from the time of initial documentation of response to the time of disease relapse or death due to any cause, whichever occurs first. Patients who are still in response at study completion without alternative therapies will be censored at the time of their last disease assessment.

Duration of response will be calculated for patients who achieve the first evidence of CR or CRh as primary analysis. A separate exploratory analysis will be conducted for patients who achieve the first evidence of complete response (CR, CRh, CRi [CRn, CRp], or MLFS).

DOR (months) = (date of event [disease relapse or death] or date of censoring –date of first evidence of response + 1) / (365.25/12)

Sensitivity analyses will be done for duration of response by using the additional censoring rules below:

- Censored at the date of HSCT.
- Censored at the date of other alternative therapies such as surgery, procedure, radiation and subsequent antileukemic therapy, etc.
- Patients with two or more consecutive missing response assessments prior to event will be censored at the last date of response assessment before the missing assessments.

The duration of response will be analyzed using the KM method. The 25th percentile, median and 75th percentile time (including two-sided 95% CI) will be summarized.

Post-baseline transfusion independence is defined as no transfusion during any consecutive 56-day period on-study. Post-baseline transfusion independence will be summarized for RBC and platelet transfusion separately and in total. Transfusion dependence at baseline is defined as any red blood cell or platelet transfusions during the 28 days prior to the first dose of study drug. The rate of conversion from transfusion dependence to transfusion independence will be calculated. The rate of patients who are transfusion independent at baseline and remain independent during any 56-day post-baseline period will also be calculated.

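### The only CTCAE-graded laboratory tables start from a normal baseline and run by visit, so worsening from an abnormal baseline is not displayed and a worst grade can be missed

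*SAP*

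**What the plan says.** SAP 12.2 plans three kinds of laboratory output.

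- Ungraded summaries by visit: "Summaries of laboratory values will display descriptive statistics for numerically quantified labs".
- Shift tables: "Shift tables will be used to display the percent of patients who have a shift in their lab values from normal at baseline", continuing to each visit after baseline by CTCAE v4.0 grade.
- Listings: "Listings of all clinical laboratory data with abnormal flags will be provided by patients and tests".

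Protocol 9.5.2 gives the same shift rule, "from normal at baseline to each post-baseline visit by CTCAE v4.0 severity Grade". Neither document plans rows for patients who start at Grade 1 or higher, a worst-grade table, or a denominator for the percentage.

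Laboratory events can also reach the AE tables in SAP 12.1, which include "AEs by CTCAE Grade". Protocol 7.11.4 governs what gets there. For Grade 3 and 4 laboratory events it says "all such events should be reported as AEs or SAEs, as appropriate, unless these are considered an expected consequence of the underlying disease".

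**The concern.** A shift table exists to show how far each patient moved from where that patient started. This one has a single starting row, normal. In relapsed or refractory AML many patients can be expected to start elsewhere, above all for blood counts, and their worsening has no place in the table.

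This matters for this drug. Protocol 2.2 reports anaemia and thrombocytopenia in monkeys that rose with total exposure, and attributes the anaemia partly to killing of haematopoietic precursors. The protocol also treats a change from baseline grade as meaningful: in the ruxolitinib cohort a rise of 2 or more grades in haemoglobin or platelets is a dose-limiting toxicity (DLT). No planned table displays that quantity.

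**Working it through.** No figure in the plan needs reproducing. The check sets the passages side by side and then gives an illustrative size.

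**1. Can patients enter with abnormal values?** Yes.
- Protocol 5.1 and 5.2 set no minimum haemoglobin, neutrophil or platelet count.
- Inclusion Criterion 7 allows ALT and AST up to 2.5 times ULN, and bilirubin and creatinine up to 1.5 times ULN.
- Inclusion Criterion 10 requires recovery to Grade 1 or lower, but only for toxicity attributed to earlier chemotherapy. It leaves Grade 1 in place and does not reach cytopenia caused by the leukaemia.
- Protocol 2.1.1 describes AML presenting with "unexplained fevers resulting from anemia, leukocytosis, leukopenia or leukocyte dysfunction, and/or thrombocytopenia".
- SAP 11.2.1 plans for transfused patients: "Transfusion dependence at baseline is defined as any red blood cell or platelet transfusions during the 28 days prior to the first dose".

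**2. Where would a fall from Grade 2 to Grade 4 platelets appear?**

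| Output | Shown? |
|---|---|
| Shift table (SAP 12.2) | No; baseline was not normal |
| Descriptive summary by visit | Value contributes, without grade |
| Listing | Yes, but not summarised |
| AE tables by grade (SAP 12.1) | Only if reported as an AE |

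For the last row, Protocol 7.11.1 does treat a pre-existing event that worsens as treatment-emergent. The exception in Protocol 7.11.4 then applies to values put down to the leukaemia, and it falls mainly on patients who were already cytopenic. A worsening only to Grade 2 is reported at the investigator's discretion.

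**3. Is the worst grade captured?** Not reliably. SAP 7.1 takes the one value nearest each derived visit. Protocol Appendix 1 has Cycle 1 blood counts on Days 1 to 8 and, for inpatients, on Days 9 to 28. If the tabulated visits are the weekly ones, a nadir between them drops out. Even if every day were tabulated, separate percentages by visit do not give the number of patients who ever reached Grade 4.

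**4. Illustrative size.** Let f be the share of patients abnormal at baseline for one parameter. The documents do not give f; the range 50% to 95% is an assumption. The safety population is everyone dosed. Planned enrolment is 47 + about 283 = about 330, taken here as all treated. Patients who can appear in that parameter's shift table = N x (1 - f):
- f = 50%: 330 x 0.50 = 165
- f = 70%: 330 x 0.30 = 99
- f = 95%: 330 x 0.05 = about 17

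**5. Effect of the undefined denominator.** A percentage based on normal-baseline patients equals the percentage based on all patients divided by (1 - f). That is a factor of 1/0.50 = 2 at f = 50% and 1/0.30 = 3.3 at f = 70%.

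**The case against.** The strongest reply is that worsening from an abnormal baseline is handled elsewhere. Worsened pre-existing events count as treatment-emergent, Grade 3 and 4 laboratory events are in general reportable, and the AE tables by grade have no baseline restriction. The descriptive summaries include medians, minima and maxima, and the listings cover every patient. All of this is correct. It narrows the gap to the shift tables, but the exception in Protocol 7.11.4 keeps it from closing.

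A second reply is that table shells are left to a separate Statistical Programming Plan, which may hold full shift tables. That is possible, but the text of both documents says otherwise and would still need correcting.

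A third is that by-visit or worst-grade display is a matter of taste, and that transfusion affects either one. The transfusion point stands. On display, SAP 12.5 already plans a shift from baseline to worst by cycle for ECG interpretation, so the approach is one the SAP itself uses.

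A reader might also infer that DLT monitoring is impaired. The documents do not support that. In Protocol 4.2 the haematological DLT for the main cohort is Grade 4 neutropenia lasting at least 42 days from the start of the cycle without active AML, which neither table would show. The grade-increase DLT applies only to the ruxolitinib cohort of up to 12 patients. DLTs are listed separately, and the pause rule in SAP 13.3 does not use the shift tables. Nor is there a toxicology signal for neutrophils: Protocol 6.4.3 reports no decrease in circulating neutrophils in monkeys.

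**Conclusion.** The point holds as a gap in safety reporting. For each laboratory parameter, the only graded laboratory tables omit worsening in patients whose baseline value is abnormal, and by-visit display can lose the worst grade.

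The size cannot be stated from the documents. A reader might infer that most patients vanish from the haematology tables. That would need more than half to be abnormal for the parameter in question, which is plausible for blood counts but stated nowhere. Exclusion is also per parameter: a neutropenic patient with normal platelets stays in the platelet table. The counts of about 17 to 165 out of 330 illustrate an assumed range and are not estimates. The defect itself does not depend on f, provided some patients enter with abnormal values, which eligibility allows.

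The primary analysis, alpha, power and sample size are unaffected.

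**What to change.** In SAP 12.2 and Protocol 9.5.2, replace the shift-table sentence with a table of baseline CTCAE grade (0-4) against worst post-baseline grade for each graded parameter:

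- Present it overall and for Cycle 1.
- Use as denominator all safety-population patients with a baseline value and at least one post-baseline value for that parameter.
- Add the number and percentage with an increase of at least 1 grade and of at least 2 grades.
- Keep by-visit tables as a supplement if wanted.

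The cost is one sentence in each document and one standard shell in the Statistical Programming Plan. The data are already being collected.
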